# 9.3.3 Period of Observation

The period of observation for collection of AEs extends from the time the subject signs the ICF until the last study visit (Day 36), which is scheduled 5 weeks after the day of the surgery (day of IMP administration).

Abnormal, clinically relevant findings or observations made prior to signature of informed consent are to be recorded as medical history/concomitant disease but not as AEs.

AEs (including any change in severity or trait of the concomitant disease/ medical history) occurring in the pre-treatment period between signature of informed consent until first administration of study medication are non-treatment emergent AEs (NTEAEs).

AEs (including any change in severity or trait of the concomitant disease/ medical history) occurring from the administration of study medication until the subject's last study visit are treatment-emergent AEs (TEAEs).

If an SAE occurs in a subject after the period of observation, i.e., after the last study visit, which is considered by the investigator to be related to the study medication, this should be recorded as SAE and follow the immediate reporting process for SAEs as described

in Appendix 2. If the eCRF has been closed for the subject, the investigator should contact the sponsor to determine how to report the SAE (see also section 7.4).

#### 9.3.4 Assessment of Adverse Events

#### • Responsibilities of Investigator

AEs are assessed by the investigator in a standardized manner including, but not limited to the seriousness, severity, outcome, and causality. This has to be performed in line with the definitions and provisions given in Appendix 1.

Laboratory values outside the reference range have to be assessed for clinical relevance taking into account the pre-treatment values. For reporting of abnormal laboratory values as AEs refer to section 9.2.1.4.

If an AE meets the definition of any of the mandatory AE related stopping rules (section 9.3.1), the investigator must withdraw the subject and report the AE as IRAE according to section Appendix 2. If no mandatory AE related stopping rules defined for the study, delete this sentence.

For all AEs the causality assessment has to be provided in the eCRF, even if based on preliminary data. Once more information is available, the investigator may change a preliminary causality assessment.

During and after participation of a subject in a clinical study the investigator/institution has to ensure that adequate medical care is provided to the subject for any ongoing AEs including clinically significant abnormal laboratory values. The investigator has to inform the subject when medical care is needed for any intercurrent disease of which the investigator becomes aware.

# • Responsibilities of Sponsor

AEs are reviewed and assessed by the sponsor during ongoing safety monitoring activities throughout the study, as well as medical evaluation and regulatory assessment for reportability of SAEs and IRAEs. For the purpose of regulatory reporting, the causality assessment given by the investigator will not been downgraded by the sponsor. If the sponsor disagrees with the investigator's causality assessment, both the opinion of the investigator and the sponsor will be recorded.

Regulatory assessment of an AE by the sponsor comprises further the assessment of expectedness. For BT524, Fibrinogen Concentrate from Human Plasma, it is based on section 7.9 of the Investigator's Brochure (IB). For cryoprecipitate it is based on the Summary of Product Characteristics of a reference product: Reference Safety Information (RSI) for the cryoprecipitate is the section 4.8 of the SmPC of PPD solution for infusion (PPD

# • Follow-up of Adverse Events

AEs should be followed up to determine the outcome.

AEs that are serious or severe or considered related to the study medication or study procedures must be followed up by the investigator until the AE is resolved or resolved with sequelae, and until all queries related to the AE have been Study No.: 995

clarified. If the subject had an AE with fatal outcome, an autopsy report should be provided if possible.

If AEs that are serious or severe or considered related to study medication or study procedures are ongoing at the time of the subject's last study visit, or if the subject has clinically relevant laboratory parameter abnormalities at the last study visit, one or more safety follow-up visit should be scheduled for those subjects. The investigator should set the interval to the additional safety follow-up visit according to his/her medical judgment. Follow-up activities should be continued until the investigator considers it medically justifiable to stop further follow-up.

All other AEs must be followed up by the investigator until the AE is resolved or resolved with sequelae or the end of the period of observation (= last study visit), whichever comes first.

The investigator should respond to any queries raised by the sponsor in relation to AEs, including provision of supporting documentation for SAEs or other IRAEs (e.g. ECG data, laboratory results, hospital summary, autopsy report) within the requested timeline. In case of fatal or life-threatening SAEs the sponsor may request urgent clarification within one calendar day. In general, if for AEs requiring immediate reporting from investigator to sponsor (IRAE/SAE) follow-up information becomes available, this must be reported to the sponsor within 24 h of becoming aware of this information (i.e., the same timeframe as for initial IRAE/SAE reports). Any supporting documents have to be identified by the subject ID, and personal data (e.g. subject name, address or phone number) obliterated prior to sending to the sponsor. For details on reporting IRAE/SAE see Appendix 2.

AE data in the eCRF must be updated accordingly when follow-up information is received.

All efforts to collect follow-up information must be documented in the subject's source data.

Subjects who were treated with the study medication but did not complete the study as per protocol, should receive all the examinations and investigations scheduled for the last study visit. The investigator should make all efforts to contact subjects lost to follow-up and document the attempts in the subject's source data.

9.3.5 Immediate Reporting by Investigator to Sponsor (also refer to Appendix 2: Reporting Procedures)

9.3.6 Use of IMP outside the Specifications of the Clinical Study Protocol

Situations may occur where the IMP is used outside the specifications of the protocol, which may or may not be associated with an AE. These special situations comprise

- Medication errors (including overdose)
- Abuse/ misuse of the IMP. •

Such situations, whether or not associated with an AE, are documented in the eCRF on dedicated pages. Any AE that occurred in association with such a special situation has to be cross-referenced on the dedicated eCRF page. An IRAE/SAE occurring in conjunction with a medication error or abuse/ misuse of the IMP has to follow the

PPD
immediate reporting process for IRAE/SAE as described in Appendix 2 in addition to its documentation in the eCRF (also refer to sections 9.3.8 and 10.2).

# 9.3.7 Investigational Medicinal Product Complaints

IMP complaints must be recorded in the eCRF and in addition reported to the sponsor on the "Investigational Medicinal Product Complaint Report Form" within 24 hours of the investigator becoming aware of the IMP complaint. If the IMP complaint is associated with an AE, the AE must be entered in the eCRF also.

Any complaint samples should be provided to the sponsor upon request.

## 9.3.8 Special Situations Requiring Immediate Reporting

Special situations may occur that may or may not be associated with AEs. For these situations special reporting provisions apply.

Special situations comprise:

- Pregnancy in a female study subject or the partner of a male study subject
- Investigational Medicinal Product Complaint.
- Use of IMP outside the specifications of the CSP (e.g. Medication errors, overdose, misuse and abuse (also refer to sections 9.3.6 and 10.2).
- Protocol deviations (refer to section 10.2)

If such a situation occurs, the investigator should contact the sponsor immediately. A special paper report form has to be completed always in these situations and sent to the sponsor immediately, but not later than 24 hours after the investigator becoming aware of the situation.

## 9.3.8.1 Pregnancy

Pregnant women are excluded from the study, and female study subjects of child-bearing potential undergo pregnancy testing at screening and regularly during the study (section III, Flowchart of study). If pregnancy is suspected in a study subject during treatment with the IMP, the IMP must be immediately withheld until the result of a confirmatory test is available. If confirmed, the subject must be withdrawn from the study. Furthermore, the reason and the contraception methods may need to be reviewed and documented as a preventative measure for other participants.

Reliable methods of contraception are

- combined (estrogen and progestogen containing) hormonal contraception associated with inhibition of ovulation,
- progestogen-only hormonal contraception associated with inhibition of ovulation,
- intrauterine device (IUD),
- intrauterine hormone-releasing system (IUS),
- bilateral tubal occlusion,
- vasectomised partner,
- sexual abstinence only when abstinence is the usual and preferred lifestyle of the subject.

Although not an AE per se, pregnancy in a female study subject or the partner of a male study subject must be recorded if it occurs during the period of observation of the study (see definition in section 9.3.3). The investigator must contact the sponsor immediately in such a situation.

The pregnancy must be documented on a "Drug Exposure Via Parent" (DEVP) Report Form and reported to the sponsor within 24 hours of the investigator becoming aware of the pregnancy. If an AE occurs in relation to the pregnancy, it has to be noted on the DEVP form and recorded in the eCRF. If an IRAE/SAE occurs in relation to the pregnancy, it has to be noted on the DEVP form and recorded in the eCRF and follow the immediate reporting process for IRAE including SAE as described in Appendix 2.

The investigator must make all reasonable efforts to follow up the pregnancy until its end and will report all outcomes associated with the pregnancy to the sponsor. In the situation of pregnancy of the female partner of a male study subject, consent for the release of medical data should be obtained from the female partner to allow collection of information on the outcome of the pregnancy.

## 9.4 Data Safety Monitoring Board

A DSMB will independently monitor the study.

The DSMB will independently review and assess the unblinded safety data throughout the entire study at regular intervals. The DSMB consists of three voting members: an expert in pharmacovigilance, an expert in the field of hematology/hemostaseology and an expert in anaesthesiology. Two members of the DSMB constitute a quorum.

In addition, a statistician without a vote will be responsible for adequate data supply. Prior to the data safety monitoring phase, a meeting will be held to familiarize the DSMB with all relevant procedures. The DSMB members are unblinded during both evaluation periods and will be provided with the following information: reports of SAEs and AEs, data on markers of coagulation and coagulation factors, clinical laboratory assessments of hematology, clinical chemistry and urinalysis, and vital signs.

DSMB meetings will take place at regular intervals. The DSMB will be provided with data covering the screening visit, the day of surgery plus 4 additional follow-up visits (Day 2, 3, 5 and 8) and will evaluate the subjects' risks at a formal DSMB meeting with regards to the relevant parameters and outcome criteria. In addition, subject's data from the closing visit will also be evaluated if data already available at the time of the DSMB meeting. After each meeting treatment of the following subjects can continue unless the DSMB has not actively disapproved it.

Minutes of the DSMB will describe the proceedings from all sessions of the DSMB meeting, and will summarize all recommendations, which will also be reported to Biotest and the principal investigator.

The DSMB members can propose to stop the study at any time after a scheduled or unscheduled meeting in case of major safety concerns related to study treatment.

Further details will be provided in the DSMB Charter.

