## 10.8 Interim Analyses

In this study, 3 interim analyses of the observed blood losses are planned to have the option of adjusting the sample size needed (primary: PPS, secondary: FAS).

For this purpose, an alpha-adjustment according to Haybittle/Peto (Haybittle, 1971; Peto et al., 1976; Schulz and Grimes, 2005) is planned. This leads to local alpha levels of 0.001 for each interim analysis and a significance level of 0.05 for the final analysis to reach a global significance level of 5%.

All interim analyses will be based on the PPS.

The first interim analysis is planned with approximately 50 spine subjects, the second one with at least 40 PMP subjects and all other evaluable spine subjects at that time-point. The third interim analysis is planned after approximately 80% of subjects of the total sample size.

Aim of all interim analyses is to adapt the sample size according to the observed blood losses and the standard deviations:

- a.) Early termination due to non-inferiority of BT524 in comparison with the used standard therapies.
- b.) Continuation with the sample size as initially planned.
- c.) Adjustment of sample size to take into account changes from the previous assumptions on the additional blood loss.
- d.) Stopping the study early due to futility if the sample size re-estimation indicates a much higher number than planned before.

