# Final 4.3\_UK

# **15 APPENDICES**

Appendix 1: Safety Definitions Appendix 2: Reporting Procedures

#### Appendix 1: Safety Definitions

#### • Adverse Event (AE)

Any untoward medical occurrence in a patient or clinical study subject administered an IMP and which does not necessarily have a causal relationship with this treatment. An AE may be any aggravation or new unfavorable and unintended sign, symptom, or disease temporally associated with the use of an IMP, whether or not considered related to the IMP.

This includes abnormal laboratory and other investigation results which are considered clinically relevant by the investigator (unless already pre-existing at baseline). However, if an abnormal laboratory value is a sign of an already reported AE (e.g. infection), the respective abnormal laboratory value does not constitute a separate AE.

A surgical or invasive procedure is not an AE in itself. Instead, the condition for which the surgical or invasive procedure is performed may be an AE. Planned or elective surgery or procedures (i.e. planned prior to signature of informed consent) for a pre-existing condition and the pre-existing condition leading to surgery or procedure are not AEs. However, if the pre-existing condition worsened after signature of informed consent, the worsening of the condition constitutes an AE.

Worsening of the disease under study (underlying disease): This will be captured by efficacy parameters and should not usually be recorded as AE, unless one or more of the following criteria are met:

- The worsening of the disease under study constitutes a serious AE
- A deterioration exceeding the usual fluctuations of the disease under study has occurred in the opinion of the investigator
- The worsening leads to discontinuation of the study medication
- Additional treatment is required for the worsening, e.g. concomitant medication is added or changed.

No causal relationship with the investigational drug, or comparator drug, or study procedures is implied by the use of the term "Adverse Event".

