At each interim analysis, the tables and listings which are specified in the document: Biotest 995 TFL Specifications for Interim Analysis of Sample Size (see Appendix 1) will be produced.

For the interim analysis, the sample size will be recalculated according to the observed blood losses and the SDs using nQuery Advisor version 4.0 or higher.

The interim analysis will be based on unblinded data. The analysis will be performed by an Independent Interim Analysis Team. The interim analysis outputs will be created in a secure, restricted-access storage area on the PPD SAS file-server. All derived datasets, analysis outputs, email communications, etc. created as part of an interim analysis and containing the potential to unblind or result in operational bias, must be handled in a manner such that the Project Team has no access to them. The Independent Reporting Statistician files the final datasets, and any email communication in a secure, restricted-access storage area.

The Independent Reporting Statistician shares only the newly calculated sample size and the recommendation (see rules above) from the interim analysis results with the Sponsor and PPD study team.

In the final BDRM meeting the need for additional subgroup definitions related to length between decision to treat and end of surgery will be evaluated. If required, additional subgroups will be added to the SAP and shells in a new SAP version prior to database lock and the final evaluation.

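### The DSMB data list omits blood loss, rebleeds and transfusions by arm, the interim looks have no harm outcome, and the DSMB continuation rule is inverted as written

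*Protocol*

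**What the plan says.** Protocol 9.4 sets the DSMB's remit: "The DSMB will independently review and assess the unblinded safety data throughout the entire study at regular intervals". Its members "will be provided with the following information: reports of SAEs and AEs, data on markers of coagulation and coagulation factors", and the list then continues with haematology, clinical chemistry, urinalysis and vital signs. The DSMB "will evaluate the subjects' risks at a formal DSMB meeting with regards to the relevant parameters and outcome criteria", but the outcome criteria are not named. Further detail is left to a DSMB Charter. The section's only continuation rule reads: "After each meeting treatment of the following subjects can continue unless the DSMB has not actively disapproved it".

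The flowchart and section 7.1 show that intra-operative blood loss, 24-hour drainage, rebleeding episodes and transfusion products are all recorded. Section 9.2.3 makes virus status a safety endpoint, yet it too is absent from the 9.4 list.

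Blood loss by arm is examined at three interim analyses (Protocol 10.8, SAP 10.0), run on unblinded data by an Independent Interim Analysis Team. There are four outcomes: (a) stop for non-inferiority, (b) continue, (c) change the sample size, and (d) "Stopping the study early due to futility if the sample size re-estimation indicates a much higher number than planned before". The reporting statistician "shares only the newly calculated sample size and the recommendation (see rules above) from the interim analysis results with the Sponsor" and the study team. The DSMB is not named as a recipient.

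**The concern.** BT524 replaces a haemostatic standard of care, so if it works less well the patient bleeds more. The body charged with patient safety is not listed to see the direct measures of that. The group that does see them is set up to resize the trial, not to judge harm. A moderate excess of blood loss or transfusion use on BT524, below the level that produces reportable events, could therefore be present in the data without anyone being asked whether it is acceptable for patients.

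The continuation sentence is a separate, smaller matter. Taken literally, treatment goes on only if the DSMB has disapproved. The intention is easy to recover, but this is a safety rule and it should say what it means.

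**Working it through.** **1. What reaches the DSMB, by data item**

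| Item | Collected | On the 9.4 list | Other route to the DSMB |
|---|---|---|---|
| Intra-operative blood loss | Yes | No | Only if it leads to a reportable event |
| 24-hour blood loss | Yes | No | Same |
| Rebleeds | Yes | No | By definition need haemostatic treatment, so many should appear as adverse events |
| Transfusions | Yes | No | Partly: unplanned blood products count as corrective treatment in the bleeding AESI (9.3.1) |
| Virus status | Yes | No | Suspected transmission is an AESI (9.3.1) |
| Haemoglobin, vital signs | Yes | Yes | – |

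Appendix 1 says of worsening of the disease under study: "This will be captured by efficacy parameters and should not usually be recorded as AE". It then lists exceptions: a serious event, deterioration beyond usual fluctuation, discontinuation of study medication, or a need for additional treatment. Severe or treated bleeding therefore enters the adverse event data. A difference between arms in millilitres lost, or in red cells given under institutional practice, need not.

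**2. The plan's own sample size**

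Inputs (Protocol 10.9): margin 150 mL, SD 375 mL, one-sided alpha 2.5%, power 80%. The plan states no true difference; zero is assumed here.

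n per arm = 2 × (1.960 + 0.842)² × 375² / (150 − d)². The numerator is 2 × 7.849 × 140,625, about 2,207,500. At d = 0, n = 2,207,500 / 22,500 = 98.1, so 99. The t distribution gives 80.4% power at 100 per arm, so the stated 100 reproduces.

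**3. Precision at the interims**

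SE of the difference = 375 × √(2 / n per arm), with equal arms.

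- First interim, about 50 subjects (25 per arm): 375 × √0.08 = 106.1 mL.
- Third interim, 80% of 200 (80 per arm): 375 × √0.025 = 59.3 mL.

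An observed excess on BT524 of about 1.96 × 106.1 = 208 mL at the first look, or 1.96 × 59.3 = 116 mL at the third, would lie 1.96 SE above zero. These figures show what the data could resolve; they are not proposed boundaries.

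**4. How the four outcomes would respond to an excess**

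The documents say the size is adapted to the observed blood losses and SDs. They do not say outright that the observed difference is used as d. If it is, with the SD kept at 375 mL:

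| Observed excess on BT524 (mL) | n per arm |
|---|---|
| 0 | 99 |
| 25 | 142 |
| 50 | 221 |
| 75 | 393 |
| 100 | 883 |
| 125 | 3,532 |
| 150 or more | none exists |

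With a true excess of 200 mL, the chance of observing at least 150 mL is Φ(50 / 106.1) = 68% at the first look and Φ(50 / 59.3) = 80% at the third. With no true difference it is 8% and 0.6%. Outcome (d) would thus often respond to a large excess, but as futility. For excesses of about 25 to 75 mL, whether the result is enlargement under (c) or a stop under (d) depends on a threshold that is not given.

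**The case against.** A reader might infer that nobody is charged with acting on worse bleeding. The documents do not support that.

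- Bleeding that causes severe anaemia, hypotension or shock and needs immediate correction is an AESI, reportable within 24 hours (9.3.1). The Appendix 1 exceptions bring in other treated or serious bleeding.
- Section 13.3 has the DSMB ensure that continuing the study is appropriate. Section 9.4 lets it propose a stop at any time for major safety concerns.
- Section 7.3.1 lets the sponsor stop for lack of efficacy or a changed benefit-risk ratio.

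Two further inferences also fail. A large excess, say 300 mL, would not plausibly lead to enlargement: if the observed difference drives the re-estimation, no finite size exists and outcome (d) applies. Nor can one say that an early non-inferiority stop would come without DSMB safety review, because the DSMB reviews unblinded safety data throughout; what is missing is a stated link to the interims.

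The Charter and the DSMB table specifications, cited in 9.4 and in SAP 10.0 and Appendix 1 but not available here, may already contain the missing items. An independent interim team separate from the DSMB is a legitimate arrangement.

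All of this stands, and it limits the point. It does not remove it. The event routes catch consequences of bleeding, not the comparative measurement. The sponsor's power is discretionary, and from the interims the sponsor receives only a sample size and a recommendation. If the Charter supplies the data, 9.4 should say so.

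**Conclusion.** The concern holds in a limited form. No body is assigned by-arm blood loss, rebleed and transfusion data together with a mandate to judge harm. The DSMB has the mandate without those data on its list; the interim team has blood loss without a harm outcome, and its futility trigger is unquantified. The exposed range is a moderate excess that stays below reportable events and short of the 150 mL at which re-estimation breaks down.

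The millilitre figures assume SD 375 mL, equal arms, approximate normality and, for the re-estimated sizes, use of the observed difference. The conclusion about the data list rests on the protocol and SAP text alone; the Charter could narrow it.

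This is a cheap improvement to patient protection, not a flaw in the primary inference. The continuation sentence is simply wrong as written.

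**What to change.** 1. In Protocol 9.4, and in the Charter and DSMB table list if not already there, add intra-operative and 24-hour blood loss, rebleeds and transfusions by arm and by surgery type, plus virus status.
2. In Protocol 10.8 and SAP 10.0, state that for any remaining interim the by-arm blood-loss output also goes to the DSMB for a non-binding safety review. Any criterion is for the sponsor and DSMB to set. Give a number to the futility trigger in outcome (d).
3. In 9.4, delete the stray negative so that treatment of later subjects can continue unless the DSMB has actively disapproved it.

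The cost is wording in the protocol, Charter and SAP; the data and an unblinded statistician already exist. The downside is that the DSMB sees unblinded efficacy data. A review that can only lead to a pause or stop for harm does not raise the type I error for non-inferiority. SAP 10.0 refers to past interim analyses, so for looks already done only documentation is possible: record what the DSMB saw and when.
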